#### End of Therapy

- History
- Physical exam: vital signs, height, weight, body surface area
- Performance status: Lansky/Karnofsky (Appendix I)
- Hematology: complete blood count, differential
- Serum Chemistry: ALT, AST, alkaline phosphatase, bilirubin, BUN, creatinine, electrolytes, calcium, magnesium, phosphorus, total protein, albumin, serum creatinine phosphokinase.
- Fasting\* glucose and Fasting serum lipid profile (triglycerides, total cholesterol, HDL and LDL) \*Fasting = 12 hours prior to glucose testing and lipid testing
- Patient diary

### **10.3. OFF STUDY EVALUATIONS**

The following studies should be performed, if feasible, at the time a patient is removed from the study:

- History
- Physical exam: vital signs, height, weight, body surface area
- Performance status: Lansky/Karnofsky (Appendix I)
- Hematology: complete blood count, differential
- Serum Chemistry: ALT, AST, alkaline phosphatase, bilirubin, BUN, creatinine, electrolytes, calcium, magnesium, phosphorus, total protein, albumin, serum creatinine phosphokinase.
- Radiologic imaging: Evaluation of other measurable or evaluable disease sites by appropriate radiological evaluation (i.e. CT scan, MRI)

## STUDY CALENDAR

Studies to be obtained	Pre-treatment 	During Cycle 1	Prior to subsequent cycles	End of therapy
History and Physical with vitals	X	Weekly	X	X
Performance status (Karnofsky)	X		X	X
CBC, differential	X	Weekly 	X 	X 
Serum Chemistry 	X	Weekly	X	X
Fasting glucose and serum lipid profile 	X		X	X
Urine or serum pregnancy  test	X		X	
Echocardiogram or cardiac MRI and ECG	X 		Prior to cycles 6 and 12, and every 6 cycles	
FDG-PET	X 	Day 11 +/- 3 days		
Ophthalmology Exam	X		Prior to cycles 6 and 12 and every 6 cycles	
Tumor Evaluation (by CT, MRI)	X 		Prior to cycles 3,5,7 and then every 3 cycles	
Patient reported pain	X		Prior to cycles 2, 3, 5, 9, 13, and then every 6 cycles	
Patient Diary		Weekly	X	X
Pharmacodynamic/Immune Markers 	X	Day 15 (up to day 28) 	ctDNA only: prior to cycles 3, 5, 7 and then every 3 cycles	
Tumor biopsy 	X	Day 15 (up to day 28) 		
Genomic testing 	X	Day 15 (up to day 28) 		

 See Section 3.2

For patients who experience Grade 4 ANC or platelets, check CBC q 3-4 days until  $\geq$  Grade 3

Sodium, potassium, chloride, bicarbonate, calcium, phosphorus, magnesium, creatinine, glucose, blood urea nitrogen, total protein, SGOT (AST), SGPT (ALT), total bilirubin, alkaline phosphatase, uric acid.

Fasting = 12 hours prior to testing. Glucose and serum lipid panel (triglycerides, total cholesterol, HDL, LDL)

 For females of child-bearing potential

Can be done within 4 weeks prior to enrollment.

 For serum and/or tissue samples, See Section 2.5

 Tumor biopsy is optional and will be collected only for patients who provide written consent and has tumor accessible to percutaneous biopsy

 Baseline blood will be (mandatory) collected and for patients who provide written consent and has tumor accessible to percutaneous biopsy may be collected at baseline and day 15 per patient consent

 Will be collected during cycle 1 on any one day on or after day 15 (i.e. one day between day 15-28)

## 11. MEASUREMENT OF EFFECT

### 11.1. Antitumor Effect – Solid Tumors

For the purposes of this study, patients should be re-evaluated for response prior to every odd cycle.

Response and progression will be evaluated in this study using the new international criteria proposed by the revised Response Evaluation Criteria in Solid Tumors (RECIST) guideline (version 1.1) [65]. Changes in the largest diameter (unidimensional measurement) of the tumor lesions and the shortest diameter in the case of malignant lymph nodes are used in the RECIST criteria.

#### 11.1.1. Definitions

Evaluable for PET response: Patient must have FDG-PET performed at time points stated in protocol to be evaluable for PET response. PET response will be measured by PERCIST 1.0 (see section 11.1.6).

Evaluable for objective response: Any patient who is enrolled and receives at least one dose of selumetinib and one dose sirolimus will be considered evaluable for response provided: (1) the patient demonstrates progressive disease or death while on protocol therapy; or (2) the patient is observed on protocol therapy for at least one cycle and the tumor is not removed surgically prior to the time complete response or partial response is confirmed; or (3) the patient demonstrates a complete or partial response or stable disease as confirmed according to protocol criteria. The evaluation period for determination of best response will be 6 treatment cycles. All other patients will be considered non-responders.

Evaluable for toxicity: All patients who receive at least one dose of selumetinib or sirolimus and either experience a toxicity or complete the first cycle with no toxicity will be considered in the evaluation of toxicity.

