### **1.2. Secondary Objective(s)**

- To define and describe the toxicities of selumetinib in combination with sirolimus in patients with unresectable or metastatic NF1 associated or sporadic MPNST.
- To assess the impact on intensity and pain interference and correlate to changes in clinical, imaging response and progression
- To assess progression free and overall survival

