#### 5.1.2. Sirolimus

Sirolimus will be purchased commercially (2mg tablets) and administered once daily. On cycle 1 on day 1, a loading dose of sirolimus will be given orally x 1. Subsequent doses of sirolimus will be 4mg given orally once daily continuously with no breaks in between cycles. Sirolimus should be taken around the same time as the morning dose of selumetinib. Sirolimus should be taken at approximately the same time every day. If a patient misses a dose, the dose may be taken within 4 hours of missed dose. Otherwise, patient must wait until the next day's dose. If a patient vomits after a dose of sirolimus it will not be repeated. Tablets must be swallowed whole. All doses prescribed and dispensed to the patient and all dose changes during the study will be recorded in the patient diary.

One cycle of therapy is 28 days.

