## 5.6. Duration of Follow Up

Patients will be followed for adverse event(s) until 30 days after last treatment or until resolution or stabilization of the adverse event (whichever comes last). Patients who are removed from protocol therapy for a reason other than disease progression, should be followed up every 6 months by imaging to monitor disease status. Every effort should be made to collect information regarding disease status until the start of new anti-cancer therapy, disease progression, or death. Once a patient experiences confirmed disease progression or starts a new anti-cancer therapy, the patient should be contacted by telephone every 6 months to assess for survival status until death or withdrawal of consent or end of study, whichever occurs first.

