## 7.2. Handling of Safety Parameters

### 7.2.1. Reporting of Adverse Events

All adverse events (related and unrelated)  $\geq$  Grade 3 occurring during the study and up to 30 days after the last dose of study medication must be reported.

Reporting the specific time of onset of a given AE is only necessary when it occurs in relation to study drug administration.

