### **13.4. Analysis of Secondary Endpoints**

Summary statistics will be used to describe the study population and baseline characteristics.

Progression free survival will be determined using the Kaplan-Meier method, with PFS at important time points (6 or 12 months for example) reported along with 95% two sided confidence intervals.

Toxicities to be summarized descriptively and tabulations on the type, severity, and relationship to study treatment will be performed.

Changes in FDG-PET avidity, tumor biomarkers, pain severity and pain interference ratings, and immune markers will be exploratory and summarized using descriptive statistics and when feasible compared using Wilcoxon rank test or pairwise t-test. Correlations to imaging response, toxicity, and immune markers will be made if feasible.

The comprehensive genomic analyses including next generation sequencing and ctDNA analysis will be performed in the Oncogenomics laboratory ([name]/NCI). Bioinformatics analysis will be primarily performed at the NCI using well-established pipelines previously developed.

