### **13.5. Adverse event stopping rule**

If in the first 7 patients, 3 or more patients experience a grade 4 or higher non-hematologic adverse event, the study team will suspend accrual (if the trial is still accruing) and do a thorough analysis of the adverse events. If the grade 4 or higher events are felt to be at least possibly related to the study treatment, the study team, in consultation with SARC scientific leadership will make a recommendation to the sponsor to either alter the dose level of one or more of the drugs or to stop the trial due to toxicity. All participating IRBs will be notified of the adverse event and the recommendation.

At any point after 8 or more patients are enrolled, 1/3 or more of the patients experience a grade 4 or higher non-hematologic adverse event felt to be at least possibly related to the study treatment, the study team will suspend accrual to evaluate the adverse events. In consultation with the SARC scientific leadership, the study team will recommend that the trial continue without modification, alter the dose level of one or more of the drugs, or to stop the trial due to toxicity. The recommendation will be made to the sponsor and all participating IRBs will be notified of the adverse events and the recommendation.

Adverse events are reviewed on at least a monthly basis by the study team and the SARC Clinical Trial Review Committee and the trial will stop accrual if the adverse event stopping boundary is crossed.

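### The toxicity-evaluable set counts a patient who stops in cycle 1 only if a toxicity occurred, so the toxicity denominator depends on the outcome

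*Combined protocol and SAP*

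**What the plan says.** Section 11.1.1 (Definitions) admits a patient to the toxicity evaluation on two conditions. The patient must have taken a dose of either study drug, and must "either experience a toxicity or complete the first cycle with no toxicity". It gives no grade or attribution threshold for what counts as a toxicity.

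Section 1.2 makes toxicity a secondary objective: "To define and describe the toxicities of selumetinib in combination with sirolimus". The planned analysis in Section 13.4 is descriptive: "Toxicities to be summarized descriptively and tabulations on the type, severity, and relationship to study treatment will be performed". That section names no denominator, and no safety set of all treated patients is defined elsewhere.

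Three other places bear on the point:

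- **Follow-up.** Section 5.6 says "Patients will be followed for adverse event(s) until 30 days after last treatment or until resolution or stabilization of the adverse event", whichever is later. Section 7.2.1 requires that adverse events of Grade 3 or higher "occurring during the study and up to 30 days after the last dose of study medication must be reported". Section 5.1.2 gives the cycle length: "One cycle of therapy is 28 days".
- **Recording.** Section 7.1.1.3 says that the intensity of all adverse events is graded from 1 to 5 and recorded in detail on the CRF.
- **Safety monitoring.** Section 13.5 counts the first 7 patients and then uses a different base: "At any point after 8 or more patients are enrolled, 1/3 or more of the patients". Its boundary summary refers to patients accrued.

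**The concern.** A patient who takes study drug and leaves during cycle 1 is kept in the toxicity set if a toxicity occurred and dropped if not. Every dropped patient contributes nothing to the count of qualifying toxicities but would have contributed to the denominator. The selection therefore works in one direction only.

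Exits during cycle 1 are plausible. Section 2.1.3 describes a median time to progression of under 2 months in earlier targeted-agent trials, Section 3.1.8 admits patients with a performance level of 50%, and Section 5.5 allows removal for clinical progression, refusal or a concurrent medical condition.

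At stake is the accuracy of the descriptive toxicity rates. In a trial of at most 21 patients, each excluded patient moves those rates visibly. Because toxicity is not defined in Section 11.1.1, two analysts could also build different sets from the same data.

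**Working it through.** **Inputs.** Maximum N = 21, as 7 + 14 (Synopsis and Section 13.1). Cycle length 28 days (Section 5.1.2). Adverse event follow-up of at least 30 days after last treatment (Section 5.6). The number k of dosed patients who stop in cycle 1 without a toxicity is not in the documents; I take k = 1 to 3 as an assumption.

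**The plan's own figures.** The plan states no toxicity rate, so the only figure to reproduce is the design that gives N = 21. With p0 = 0.05, the probability of early termination is 0.95^7 = 0.698, and the expected sample size is 7 + (1 − 0.698) × 14 = 11.2. Both match Section 13.1. The exact two-stage calculation gives a type I error of 0.064 and power of 0.904, within the stated limits.

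**Is the exclusion needed for lack of observation?** No. Follow-up of at least 30 days after last treatment exceeds the 28-day cycle, so the plan already observes an early stopper for at least a cycle length.

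**Size.** Let x be the number of patients with a given qualifying toxicity. Excluded patients have none, so x is unchanged.

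- All treated: x/21
- Rule in Section 11.1.1: x/(21 − k)
- Ratio: 21/(21 − k), which is 21/20 = 1.05, 21/19 = 1.11 and 21/18 = 1.17 for k = 1, 2, 3

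| x | All treated (x/21) | k = 1 (x/20) | k = 2 (x/19) | k = 3 (x/18) |
|---|---|---|---|---|
| 3 | 14.3% | 15.0% | 15.8% | 16.7% |
| 6 | 28.6% | 30.0% | 31.6% | 33.3% |
| 10 | 47.6% | 50.0% | 52.6% | 55.6% |

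With k = 0 all columns are equal. Over these cases the increase runs from 0.7 to 7.9 percentage points.

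**Cross-check on the rate of any toxicity.** Assume independent exponential times to toxicity and to stopping over one cycle, counting only toxicities that precede stopping. Let F be the risk of toxicity over a full cycle 1 and d the probability of stopping in cycle 1. With a = −ln(1 − F) and b = −ln(1 − d):

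- All-treated rate: T = [a/(a + b)] × [1 − (1 − F)(1 − d)]
- Rate in the Section 11.1.1 set: T / [T + (1 − F)(1 − d)]

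| F | d | All treated | Section 11.1.1 set |
|---|---|---|---|
| 40% | 10% | 38.1% | 41.4% |
| 40% | 30% | 34.2% | 44.8% |
| 90% | 10% | 87.0% | 90.6% |

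In every scenario run (F from 20% to 90%, d from 5% to 30%), the Section 11.1.1 set gave a rate above both the all-treated rate and F.

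**The case against.** The strongest objection is that the effect may be negligible and that the remedy has a bias of its own.

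**Any-grade toxicity is common.** Section 7.3 lists rash at 72.4% and raised CK at 55.1% with selumetinib, and peripheral edema at 58% with sirolimus. These are not cycle 1 rates, but few patients on both drugs are likely to be free of every toxicity. The first planned restaging is before cycle 3, so an exit for progression in cycle 1 would be clinical or unscheduled. This stands: if events of any grade count, k is probably small.

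**The shifts are small beside the sampling error.** The exact 95% interval for 6/21 is 11.3% to 52.2%, and no test or threshold is attached to the toxicity tables. This also stands, and it is why the point is minor.

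**The all-treated rate can understate the risk under a full first cycle.** In the model with F = 40% and d = 10%, it is 1.9 points low, while the Section 11.1.1 set is 1.4 points high. This is a fair cost to name. It does not justify choosing the denominator by the outcome when the purpose is to describe the toxicities seen in treated patients.

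A reader might also infer that only events of Grade 3 or higher count, because Section 7.2.1 limits required reporting to those, and that k would then be large. The documents do not settle this: Section 7.1.1.3 has all adverse events graded and recorded on the CRF, and Section 11.1.1 sets no grade. The narrower meaning is one possible reading only. Under it, the Grade 1–2 events of excluded patients would leave the tables too, so the simple multiplier would apply only to events that qualify.

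**Conclusion.** The point holds as a minor defect in a secondary analysis. The definition selects early stoppers on the outcome, nothing else in the plan corrects it, and the planned follow-up makes the exclusion unnecessary. Rates of qualifying toxicities are multiplied by 21/(21 − k), or 1.05 to 1.17 for an assumed k of 1 to 3.

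Two stronger conclusions are tempting and are not supported. The first is that every toxicity rate will be overstated: if no patient is excluded, there is no bias. The second is that the definition could trip the safety boundary, since 6/18 equals one third and 6/21 does not. Section 13.5 is written on patients enrolled or accrued, so 6/18 is never compared with one third. The primary endpoint and the Simon design do not use this set.

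**What to change.** In Section 11.1.1, define the toxicity population as all patients who receive at least one dose of selumetinib or sirolimus. In Section 13.4, name that population as the denominator for the toxicity tables. Report alongside them how many patients stopped during cycle 1 and why, so that readers can judge incomplete exposure. It would help to state in the same place which grades and attributions count as a toxicity.

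The cost is one or two sentences and no new assessments. The small downside is that patients with incomplete exposure may bring reported rates slightly below the risk under a full first cycle; the count of cycle 1 stoppers makes that visible.

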#### 11.1.2. Disease Parameters

##### Measurable Disease:

The presence of at least one lesion that can be accurately measured in at least one dimension with the longest diameter at least 10mm (CT scan slice thickness no greater than 5mm). The investigator will identify up to 5 measureable lesions to be followed for response (maximum 2 per organ). Previously irradiated lesions must demonstrate clear evidence of progression to be considered measureable.

##### Malignant lymph nodes:

To be considered pathologically enlarged and measureable, a lymph node must be  $\geq 15$ mm in short axis when assessed by CT scan (CT scan slice thickness no greater than 5mm). At baseline and in follow up, only the short axis will be measured and followed.

#### Non-measurable disease:

All other lesions (or sites of disease) including small lesions (<10mm or pathological LN  $\geq 10$  to <15mm short axis) are considered non-measurable. Bone lesions, leptomeningeal lesions, ascites, pleural/pericardial effusion, lymphangitis cutis/pulmonitis, inflammatory breast disease, and abdominal masses (not followed by CT or MRI) are considered non-measurable.

Note: Cystic lesions that meet the criteria for radiographically defined simple cysts should not be considered as malignant lesions (neither measurable nor non-measurable) since they are, by definition, simple cysts.

‘Cystic lesions’ thought to represent cystic metastases can be considered as measurable lesions, if they meet the definition of measurability described above. However, if non-cystic lesions are present in the same patient, these are preferred for selection as target lesions.

#### Target lesions:

All measurable lesions up to a maximum of 2 lesions per organ and 5 lesions total, representative of all involved organs, should be identified as target lesions and recorded and measured at baseline. Target lesions should be selected on the basis of their size (lesions with the longest diameter), be representative of all involved organs, but in addition should be those that lend themselves to reproducible repeated measurements. It may be the case that, on occasion, the largest lesion does not lend itself to reproducible measurement in which circumstance the next largest lesion that can be measured reproducibly should be selected. A sum of the diameters (longest for non-nodal, short axis for nodal lesions) for all target lesions will be calculated and reported as the baseline sum of diameters. If lymph nodes are to be included in the sum, then only the short axis is added into the sum. The baseline sum diameters will be used as reference to further characterize any objective tumor regression in the measurable dimension of the disease.

#### Non-target lesions:

All other lesions (or sites of disease) including any measurable lesions over and above the 5 target lesions should be identified as non-target lesions and should also be recorded at baseline. Measurements of these lesions are not required, but the presence or absence or in rare cases unequivocal progression of each should be noted throughout follow up.

#### 11.1.3. Methods for Evaluation of Measurable Disease

All measurements should be taken and recorded in metric notation. The same method of assessment and same technique should be used to characterize each identified and reported lesion at baseline and during follow up.

#### 11.1.4. Response Criteria

**Complete Response (CR):** Disappearance of all target and non-target lesions. Any pathological lymph nodes whether target or non-target must have reduction in short axis to <10mm.

**Partial Response (PR):** A > 30% decrease in the sum of the diameters of target lesion, taking as reference the baseline sum diameters.

**Progressive Disease (PD):** At least a 20% increase in the sum of the target lesions, taking reference the smallest sum on study (this includes baseline if that is the smallest on study). In addition to the relative increase in 20%, the sum must also demonstrate an absolute increase of at least 5mm. The appearance of one or more new lesions is also considered progression. In the presence of SD or PR in the target disease, but unequivocal progression in non-target or non-measurable disease, the patient has PD if there is an overall level of substantial worsening in non-target disease such that the overall tumor burden has increased sufficiently to merit discontinuation of therapy.

**Stable Disease (SD):** Neither sufficient shrinkage to qualify for PR nor sufficient increase to qualify for PD, taking as reference the smallest sum diameters while on study.

#### Evaluation of Best Overall Response

Target Lesions	Non-Target Lesions	New Lesions	Overall Response	Best Response for this Category also requires:
CR	CR	No	CR	≥ 4 weeks confirmation
CR	Non-CR/ Non-PD	No	PR	
CR	Not evaluated	No	PR	
PR	Non-CR/ Non-PD/ Not evaluated	No	PR	
SD	Non-CR/ Non-PD/ Not evaluated	No	SD	Documented at least once ≥4 wks from baseline
PD	Any	Yes or No	PD	no prior SD, PR or CR
Any	PD*	Yes or No	PD	
Any	Any	Yes	PD	
* In exceptional circumstances, unequivocal progression in non-target lesions may be accepted as disease progression.				

#### 11.1.5. Duration of Response

Duration of overall response: The duration of overall response is measured from the time measurement criteria are met for CR or PR (whichever is first recorded) until the first date that recurrent or progressive disease is objectively documented (taking as reference for progressive disease the smallest measurements recorded since the treatment started, best response scan).

The duration of overall CR is measured from the time measurement criteria are first met for CR until the first date that recurrent disease is objectively documented.

Duration of stable disease: Stable disease is measured from the start of the treatment until the criteria for progression are met, taking as reference the smallest measurements recorded since the treatment started.

